12.1.2. Secondary Endpoints

Secondary endpoints will be to evaluate mesh-related complications and subject reported outcomes as safety endpoints between baseline and 36 months:

1. Incidence of mesh erosion
2. Incidence of mesh exposure
3. Incidence of de novo dyspareunia
4. Improvement in subject specific outcomes at 36 months compared to Baseline (pelvic floor symptoms (PFDI-20), QOL (PFIQ-7), sexual functioning (PISQ-12), TOMUS pain scale)
5. Assessment of subject's level of improvement, measured by the Patient Global Impression of Improvement for Prolapse (PGI-I for Prolapse)
6. Absence of re-intervention or re-surgery for recurrence or persistence of POP or mesh exposure/erosion
7. Surgical success based on the following composite outcome:
 - a. Subjective success: patient denies symptoms of vaginal bulging per PFDI-20 question 3, answering "no" or "yes" but "Not at all" bothersome (<2)
 - b. Anatomic success (in the operated compartment):
 - Anterior Segment: No anterior prolapse at or beyond the hymen or POP-Q point Ba<0
 - Apical Segment: The vaginal apex does not descend more than one-half into the vaginal canal (i.e. POP-Q point C < 1/2 TVL) for multi-compartment prolapse or POPQ point C < 0 for single compartment apical prolapse.
 - c. No retreatment for POP: No additional surgical treatment for POP in the segment(s) of the vagina treated at the index surgery or no pessary use since index surgery
8. Device or procedure-related incidence of the following: pelvic pain, infection, vaginal shortening, atypical vaginal discharge, neuromuscular problems, vaginal scarring, de novo vaginal bleeding, fistula formation and/or de novo voiding dysfunction

Definitions for the above listed adverse events are included in Section 21.2 (Definitions and Classifications). Rates of incidence for the adverse events will be stratified by primary or recurrent prolapse in both treatment groups.

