12.1.2.3. Statistical Methods

A comparison of data for all subjects will be included per the following statistical analyses to measure for secondary endpoints:

- Rate of adverse device or procedural-related effects within 6, 12, 18, 24 and 36 months
- Overall rate of adverse device or procedural-related effects within 6, 12, 18, 24, 36 months
- Comparison of adverse device or procedural-related effects between treatment groups
- Rate and severity of mesh exposure and erosion within 6, 12, 18, 24, 36 months
- Assessment of rate of adverse device or procedural-related effects in subjects with reoperation for failed prolapse repair
- Assessment of rates of/times to reoperation
- Comparison of rate of adverse device or procedural-related events in subjects with re-surgery in both treatment groups
- Assessment and comparison between groups of analgesic intake and pain scoring at post-operative 6 weeks, 12, 18, 24, 36 months. Pain score improvement will be analyzed with a paired t-test for each group on all patients and with the propensity score adjusted confidence intervals for the pain score differences between groups. Change in analgesic intake from baseline will be analyzed by McNemar's test for each group on all patients.
- Assessment of severe blood loss during surgical procedure
- Duration of surgery from operative report
- Assessment of re-treatment interventions (i.e. surgery, office-procedure, etc.)
- Assessment of days to discharge and return to normal activity
- Assessment of risk factors, including menopausal status, estrogen use, age smoking, diagnosis of diabetes, body mass index, concomitant procedures, surgeon training and experience

A comparison of data between baseline and 36 months for all subjects will be included per the following statistical analyses to measure for secondary endpoints:

- Quality of Life Assessments (PFIQ, PFDI, PISQ, TOMUS) at 6, 12, 18, 24, 36 months as compared to baseline: paired t-test will be used to compare mean QOL score improvement from baseline to 6, 12, 18, 24 and 36 months for each group.
- Comparison of Quality of Life Assessments improvements between treatment groups
- Assessment of Quality of Life in subjects with re-surgery after re-surgery
- Assessment of subject satisfaction at 6, 12, 18, 24, 36 months (PGI-I for Prolapse)

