12.3.5.2. Subjects with office-based intervention for recurrence

Adverse procedural/device event rates and QOL information will be collected for 36 months, regardless of whether or not the subject has office-based intervention for recurrence.

Event rate for each of device-related or procedure-related adverse events of specified AE type (mesh erosion, mesh exposure, dyspareunia) during the period after the intervention will be summarized by treatment group. Treatment groups will be compared using Cox regression for the event-free survival time (starting at the time of first office based intervention) with treatment arm.

For each QOL instrument, a comparison using a t-test will be performed between native tissue repair and mesh group on the basis of QOL score at the first scheduled follow-up after office-based intervention for recurrence.

A two sample t-test will be used to compare groups with office-based intervention for recurrence and without intervention within each treatment group. QOL score change will be reported from the last follow-up visit before office-based intervention for recurrence, to the next scheduled follow-up visit after office-based intervention for recurrence within each treatment group. For those subjects without recurrence, we will use baseline as the “before” time point in analysis, and the QOL data at 6 month follow-up visit as the “after” time point.

Similarly, event rate for each adverse device and procedure-related event type specified (mesh erosion, mesh exposure, dyspareunia) will be compared between subjects with office-based intervention for recurrence and those without. This will be done using a Cox regression of time to the first onset of each adverse event after the starting time to compare groups with office-based intervention for recurrence and within each treatment group. The starting time will be baseline for those subjects without intervention, and time of office-based intervention for recurrence for those with intervention.

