19.2. Anticipated Adverse Events

The following anticipated adverse events (AE) have been reported due to transvaginal prolapse kit placement, but are not limited to:

- Abscess
- Adhesion formation
- Allergic reaction, hypersensitivity or other immune reaction
- Bleeding
- Bruising/Hematoma
- Constipation/defecatory dysfunction
- Dehiscence of vaginal incision (Wound Dehiscence/Surgical Site Wound Irritation)
- Dehiscence and/or Necrosis
- Detrusor Instability
- De Novo Dyspareunia
- Edema/Erythema
- Exposure
- Erosion
- Extrusion
- Fistula

- Granulation tissue formation
- Hemorrhage
- Incontinence (Urinary)
- Infection/Sepsis potentiation
- Inflammation
- Irritation/Discomfort
- Migration of device from desired location
- Neuromuscular Events (including groin and leg pain)
- Organ perforation
- Overactive bladder
- Pain
- Recurrence
- Re-surgery
- Retained foreign body (foreign body reaction)
- Ureteric Injury
- Urinary Retention
- Urinary Tract Obstruction (Ureter Obstruction)
- Vessel/Nerve Injury/Perforation
- Vaginal Discharge (e.g. atypical)
- Vaginal shortening or stenosis, mesh and/or tissue contracture
- Sexual Dysfunction

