21.1. Reportable Events by Investigational Site to Boston Scientific

Any device-related, procedure-related, or pelvic floor-related adverse event experienced by the study subject after informed consent and once considered enrolled in the study, whether during or subsequent to the procedure, must be recorded in the CRF.

Refer to Section 19 (Potential Risks and Benefits) for the known risks associated with the study device(s).

Definitions of the adverse events included in the secondary endpoint will match the definitions created for the AUGS PFD Registry. All event definitions will be provided to the sites as part of a dictionary in the Manual of Operations.

When possible, the medical diagnosis should be reported as the Event Term instead of individual symptoms.

If it is unclear whether or not an event fits one of the above categories, or if the event cannot be isolated from the device or procedure, it should be submitted as an adverse event and/or device deficiency.

Underlying diseases are not reported as AEs unless there is an increase in severity or frequency during the course of the investigation. Death should not be recorded as an AE, but should only be reflected as an outcome of a specific SAE (see Section 21.2 for AE definitions).

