21.6. Relationship to Pelvic Floor

The investigator must assess the relationship of the AE to the pelvic floor as unrelated or related. See criteria in Table 21.6-1.

Table 21.6-1: Criteria for Assessing Relationship to Pelvic Floor

Classification	Description
Unrelated	
 No evidence that the adverse event has a relationship to the pelvic floor and supporting tissues.
Related	
 The adverse event is determined to be potentially related to the pelvic floor and supporting tissues including but not limited to lacerations, avulsions, tears, pelvic organ prolapse (cystocele, rectocele, enterocele, uterine, rectal), urinary incontinence (stress, urge), urinary voiding dysfunction (retention, obstructed voiding, incomplete emptying), fecal incontinence (urgency, irritable bowel syndrome), defecatory dysfunction (constipation, obstipation, stool trapping, IBS), pain (dyspareunia, pelvic, perineal), and infection (bladder, urinary tract, vaginal). There is a strong relationship to the pelvic floor and supporting tissues, and another etiology is unlikely, or There is no other reasonable medical explanation for the event.

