21.7. Investigator Reporting Requirements

The communication requirements for reporting to BSC are as shown in Table 21.7-1.

Table 21.7-1: Investigator Reporting Requirements

Event Classification	Communication Method	Communication Timeline
Serious Adverse Events related to the study device, procedure and/or pelvic floor or events resulting in death regardless of relationship to the device, procedure or pelvic floor.	Complete AE CRF page with all available new and updated information.	
 Within 2 business days of first becoming aware of the event or as per local/regional regulations. Reporting required through the end of the study.
	If requested by Sponsor, provide all relevant source documentation (unidentified) for the reported event.	
 When documentation is available

Table 21.7-1: Investigator Reporting Requirements

Event Classification	Communication Method	Communication Timeline

Adverse Events related to the study device and/or procedure. Events assessed for reporting shall include but are not limited to:
 
 • Pelvic pain • Infection (by type) • De novo dyspareunia • Vaginal shortening • Vaginal scarring • De novo vaginal bleeding • Atypical vaginal discharge • Fistula formation • De novo voiding dysfunction (including de novo incontinence) • Neuromuscular problems (including groin and leg pain) • Revision/re-surgery • Recurrent prolapse • Mesh exposure • Mesh erosion 	
Complete the AE CRF page, which contains such information as onset date of the AE, treatment provided if any, resolution, assessment of seriousness, and relationship to study device.
	
 • In a timely manner (e.g., recommended within 10 business days of first becoming aware of the event). • Reporting required through end of subject participation.

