
Adverse Events related to the pelvic floor. Events assessed for reporting shall include but are not limited to:
 
 • Urinary tract infections • Pelvic organ prolapse • Urinary incontinence • Fecal incontinence • Pelvic Pain 	
Complete the AE CRF page, which contains such information as onset date of the AE, treatment provided if any, resolution, assessment of seriousness, and relationship to study device.
	
 • In a timely manner (e.g., recommended within 10 business days of first becoming aware of the event). • Reporting required through end of subject participation.

Device Deficiencies (including but not limited to failures, malfunctions, and product nonconformities) NOTE: Any Investigational Device Deficiency that might have led to a serious adverse event if a) suitable action had not been taken or b) intervention had not been made or c) if circumstances had been less fortunate is considered a reportable event.
	
Complete CRF with all available new and updated information.
	
 • Within 1 business day of first becoming aware of the event. • Reporting required through the end of the study.

Abbreviations: AE=adverse event; CRF=case report form

21.8. *Boston Scientific Device Deficiencies*

All device deficiencies (including but not limited to complications, malfunctions, use errors, product nonconformities, and labeling errors) will be documented and reported to Boston Scientific. If possible, the device(s) should be returned to BSC for analysis. Instructions for returning the device(s) will be provided. If it is not possible to return the device, the investigator should document why the device was not returned and the final disposition of the device. Device failures and malfunctions should also be documented in the subject's medical record.

Device deficiencies (including but not limited to failures, malfunctions, and product nonconformities) are not to be reported as adverse events. However, if there is an adverse event that results from a device failure or malfunction, that specific event would be recorded on the appropriate CRF.

Any Device Deficiency that might have led to a serious adverse event if a) suitable action had not been taken or b) intervention had not been made or c) if circumstances had been less fortunate is considered a reportable event.

21.9. *Reporting to Regulatory Authorities / IRBs / ECs / Investigators*

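### Pelvic-floor-related adverse events are collected as their own class, but Section 12 plans no rate or between-arm comparison of them irrespective of device or procedure attribution

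*Combined protocol and SAP*

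**What the plan says.** **Collection.** Section 21.1 requires recording of "Any device-related, procedure-related, or pelvic floor-related adverse event experienced by the study subject after informed consent". Footnote 6 to Table 11.1-1 adds other relevant pelvic-region events. Section 21.6 sets a separate assessment: "The investigator must assess the relationship of the AE to the pelvic floor as unrelated or related". Table 21.7-1 has a reporting row for "Adverse Events related to the pelvic floor. Events assessed for reporting shall include but are not limited to" and then lists urinary tract infection, prolapse, urinary incontinence, fecal incontinence and pelvic pain.

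**Analysis.** Section 12.1.2.3 plans rates by time point, the "Overall rate of adverse device or procedural-related effects within 6, 12, 18, 24, 36 months", and a between-group comparison, all for device- or procedure-related effects. Secondary endpoint 8 (Section 12.1.2) is "Device or procedure-related incidence of the following: pelvic pain, infection, vaginal shortening" and further named events. Section 12.3.5.2 plans, after an office-based intervention for recurrence, the "Event rate for each of device-related or procedure-related adverse events of specified AE type (mesh erosion, mesh exposure, dyspareunia"); Section 12.3.5.3 repeats this after surgical intervention. Section 12.3.5.4 limits the post-re-surgery summary in the same way. Primary safety (Section 12.1.1.1) counts serious adverse device effects and serious procedure-related events, and the 12-month interim safety test (Section 12.3.8.1) uses the same definition.

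**Attribution.** Sections 21.3 and 21.4 assess relationship to the device and the delivery device in the mesh cohort only. Section 21.5 assesses relationship to the procedure in both arms. Section 12.2.2 makes single-arm centers the default and allows some mixed centers.

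**The concern.** The main safety comparisons depend on a causal judgement made event by event. The investigator making it knows which operation was done, and the plan describes no blinded adjudication; Section 22.1 provides an internal safety monitoring team, with no stated role in reclassifying events for analysis. Because most centers are meant to enroll one arm, a difference between arms in attribution habits cannot be separated from a difference between centers.

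The routes into the analysis are also unequal. A mesh event can qualify through device, delivery device or procedure; a control event can qualify only through procedure. At stake is whether the adverse-event difference reflects what happened to the women or how events were attributed. The plan collects the data that would help to tell these apart but specifies no analysis of them.

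**Working it through.** **1. The plan's own figure.** The composite in endpoint 8 is sized in Section 12.1.2.2 with a 12% rate in both arms, a margin of 8.9%, type I error 0.05 and power 80%. Taking 0.05 as one-sided:

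n per arm = 2p(1 − p)(z₀.₉₅ + z₀.₈₀)² / margin² = 2 × 0.12 × 0.88 × (1.645 + 0.842)² / 0.089² ≈ 165.

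This matches the stated 165 per arm. The point disputes no figure.

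**2. Which adverse-event analyses carry the attribution filter.**

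- Filter stated: primary safety (12.1.1.1); endpoint 8 (12.1.2); general rates, overall rate and between-group comparison (12.1.2.3); post-intervention analyses (12.3.5.2, 12.3.5.3); post-re-surgery summary (12.3.5.4).
- No filter stated: mesh erosion and exposure (12.1.2, 12.1.2.3); de novo dyspareunia as endpoint and hypothesis (12.1.2, 12.1.2.1), although the synopsis sample-size text describes it as device or procedure-related; the wording of the composite hypothesis in 12.1.2.1, although endpoint 8 itself has the filter; and the Cox regression of named events in 12.3.4.
- Pelvic-floor class named: none.

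The unfiltered analyses do not fill the gap. Erosion, exposure and dyspareunia are specific events, and the Section 12.3.4 Cox model is fitted within each group, so it does not compare arms.

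**3. Which events fall outside.** Urinary incontinence is on the list of anticipated kit events (Section 19.2: "Incontinence (Urinary")). New urinary incontinence is largely covered: Table 21.7-1 places it under "De novo voiding dysfunction (including de novo incontinence") in the device/procedure row, and de novo voiding dysfunction is a component of endpoint 8. Two cleaner examples remain:

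- Fecal incontinence is named only in Section 21.6 and in the pelvic-floor row of Table 21.7-1.
- Worsening of existing urinary incontinence is not de novo. Section 21.1 makes an underlying disease reportable once its severity or frequency increases.

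Either event enters the Section 12.1.2.3 rates if it is attributed to device or procedure. If it is attributed to neither, Section 12 gives it no adverse-event rate and no comparison by arm.

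**4. Why the bias has no fixed direction.** Let π_T and π_C be the proportions of mesh and control women with a given pelvic event, and a_T and a_C the fractions of those women whose event is attributed to device or procedure. The filtered difference is

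a_T π_T − a_C π_C = a_T(π_T − π_C) + (a_T − a_C)π_C.

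The second term depends on attribution alone. It is positive if the extra mesh-only routes make a_T larger, and negative if mesh centers attribute less readily. If a_T = a_C = a with a below 1, the difference becomes a(π_T − π_C), closer to zero, which favors a non-inferiority conclusion when π_T exceeds π_C. The documents give none of these quantities.

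**The case against.** A good deal can be said for the plan.

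- **Attribution thresholds are low.** Device-related includes possible relationships (Section 21.3), and a possible procedure relationship needs only suitable timing, even where another cause may be responsible (Section 21.5). Many pelvic events will pass. This stands and narrows the gap.
- **The assessments are not exclusive.** A reader might infer that filing an event in the pelvic-floor row of Table 21.7-1 removes it from the device/procedure analyses. It does not: that table sets reporting methods and timelines, the relationship assessments are separate, and the pelvic-floor row uses the same adverse-event form, which records relationship to the study device. The gap concerns only events held unrelated to device, delivery device and procedure.
- **Outcomes free of attribution are compared between arms.** PFDI-20, PFIQ-7, PISQ-12 and TOMUS pain are compared with propensity-adjusted intervals (Sections 12.1.2.1 and 12.1.2.3). A reader might infer that an excess of pelvic-floor events could not show anywhere; that is too strong, because these scores may reflect some of it. They are mean changes in symptoms, however, not the incidence of adverse events.
- **Tables and listings are promised.** The synopsis provides for subject summary tables and data listings of the data collected. A reader might infer that these events would go unreported; the documents do not support that. The promise names no adverse-event class and no comparison by arm.
- **Related-event analyses have a purpose.** They remove background events from both arms. That is a reason to keep them, not a reason to omit an unfiltered companion.

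**Conclusion.** The point holds in a limited form. Pelvic-floor-related adverse events are collected as a separate class, and Section 12 specifies no rate or between-arm comparison of them irrespective of attribution. The general adverse-event comparison and the main safety endpoints rest on an unblinded attribution that differs in structure between arms and is largely confounded with center.

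A reader might also infer that every planned adverse-event analysis is filtered, or that new urinary incontinence escapes testing. The unfiltered analyses in step 2 of the working, and the place of de novo incontinence within endpoint 8, rule out both.

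The size of any bias cannot be calculated, because the documents give neither a pelvic-floor event rate nor an attribution rate. The conclusion assumes that attributing investigators know the operation performed, which follows from the center-based assignment, and that no separate document adds such an analysis. It does not call the planned primary tests or their sample sizes into question. It is an inexpensive improvement to the safety reporting.

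**What to change.** Add to Section 12.1.2.3, as a supportive analysis, one table of all collected pelvic adverse events (device-, procedure- or pelvic-floor-related, regardless of attribution) by event type and arm within 6, 12, 18, 24 and 36 months. Give the propensity-adjusted difference and confidence interval of Section 12.2.3. Put recurrent or persistent prolapse on a separate line, since it is also an effectiveness outcome.

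Leave the existing device- and procedure-related analyses unchanged. In particular, do not widen endpoint 8: its 165 per arm was sized for a 12% rate, and p(1 − p) in the formula above grows as the counted rate rises toward 50%, so a broader definition would be underpowered against the same margin.

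The cost is a paragraph of SAP text and additional output from data already on the case report form. No new data, visits or subjects are needed. The downside is that attribution-free rates will be higher and will include background events in both arms, so the table should be read beside the attributed rates.

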12.2. General Statistical Methods

12.2.1. Analysis Sets

The Intent-to-Treat (ITT) subject population includes all subjects who provide written informed consent to be enrolled into the study and have a surgery initiated (i.e. incision in vagina) regardless of their adherence with the entry criteria, regardless of treatment and withdrawal/protocol deviations.

The treated population includes all subjects who undergo a study surgical procedure. The subject is defined to have successfully completed the surgical procedure (i.e. prolapse repair successful) and discharged.

The Per Protocol (PP) population includes all subjects in the ITT Population who received the assigned treatment and had no major protocol deviations.

All primary and secondary endpoints will be analyzed on the ITT Population. The primary safety and non-safety endpoints will also be analyzed on the per-protocol population.

